**Table 16                    Pre-planned statistical and sensitivity analyses to be conducted**

Endpoints analyzed	Notes
Overall survival	Primary analysis using a stratified log-rank test: Sensitivity analysis using a KM plot of time-to-censoring where the censoring indicator of the primary analysis is reversed (attrition bias)
Progression-free survival	Stratified log-rank test using Investigator assessments per RECIST 1.1
Time to progression	Stratified log-rank test using Investigator assessments per RECIST 1.1
Objective response rate	Logistic regression using Investigator assessments per RECIST 1.1
Duration of response	Analysis following the method described in Section 8.5.3, using Investigator assessments (RECIST 1.1)
Disease control rate	Summarized by treatment arm n (%) using Investigator assessments (RECIST 1.1)
Proportion of patients alive at 18 months	Hazard ratio using the KM estimates of OS at 18 months (following method described in Section 8.5.3)
Proportion of patients alive at 24 months	Hazard ratio using the KM estimates of OS at 24 months (following method described in Section 8.5.3)
Proportion of patients alive at 36 months	Hazard ratio using the KM estimates of OS at 36 months (following method described in Section 8.5.3)
CCI	

Endpoints analyzed	Notes
CCI	CCI Average change from baseline using an MMRM analysis. Summary statistics including change from baseline.

EORTC European Organisation for Research and Treatment of Cancer; CCI  
CCI KM Kaplan Meier; MMRM Mixed effect model repeat measurement; OS overall survival; PFS Progression free survival; CCI  
CCI  
CCI .

### 8.5.1 Multiple testing strategy

Two interim analyses and a final analysis are planned as described below:

IA1: The first interim analysis will be performed after approximately 100 patients per treatment arm have had the opportunity for 32 weeks of follow-up. The objective is to evaluate the efficacy of Arm A and Arm C in terms of ORR and DoR. The analysis set will include all randomized patients who have had the opportunity for at least 32 weeks of follow-up at the time of the IA1 DCO (ie, randomized  $\geq$  32 weeks prior to IA1 DCO). Descriptive summaries of ORR including exact 95% CIs will be presented for each treatment arm. KM plots of DoR and median DoR derived from the KM curves will also be provided. No formal comparison between arms will be performed in this interim analysis.

Interim Analysis 2 (IA2): The second interim analysis will be performed when approximately 404 OS events in Arm C and Arm D combined (~52% maturity), approximately 30 months after the first patient is randomized. The goal is to evaluate the efficacy of Arm C vs. Arm D (for superiority) and then Arm A vs. Arm D (for non-inferiority, then superiority) in terms of OS.

Enrollment must be completed before Interim Analysis 1 can be performed.

Final Analysis (FA): The final analysis is expected to be performed when approximately 515 OS events in Arm C and Arm D combined (~67% maturity), approximately 37.5 months after the first patient is randomized. The primary objective is to assess the efficacy of Arm C vs. Arm D in terms of OS for superiority. The key secondary objectives are to assess the efficacy of Arm A vs. Arm D in terms of OS (for non-inferiority, then superiority). Efficacy data for Arm B (which was closed for enrollment with Amendment 4) will be summarized descriptively, but will not be formally analyzed.

[figure not shown]
To strongly control the familywise error rate (FWER) at the 5% level (2-sided), an alpha level of 0.1% will be spent on the interim ORR and DoR analysis (IA1) while the remaining 4.9%

alpha level will be spent on all OS analyses. The primary objective of OS will be tested (H1: Arm C vs. Arm D) with 4.9% for this comparison.

Since two analyses of OS are planned (Interim Analysis, Final Analysis), the Lan DeMets approach ([Lan and DeMets 1983](#)) that approximates the O'Brien and Fleming spending function will be used to maintain an overall 2-sided 4.9% type I error across the two planned analyses of OS (Interim and Final) for the primary comparison (H1: Arm C vs. Arm D)

If 78% of the target OS events for H1 (ie. 404/515) are available at the time of the interim analysis, the 2-sided significance levels to be applied for the interim and final OS analyses would be and 0.0222 and 0.0425, respectively. Strong control of the type 1 error will be applied testing endpoints as outlined in the MTP (Figure 5, further details in the SAP).

Figure 5     Multiple testing procedure for controlling the type 1 error

## 8.5.2     Analysis of the primary variable(s)

### 8.5.2.1    Overall survival

The primary analysis is to compare OS for Arm C vs. Arm D (for superiority) in the FAS (ITT) analysis set.

The primary OS endpoint will be analyzed using a stratified log-rank test adjusting for etiology of liver disease (Confirmed HBV versus confirmed HCV versus others), ECOG (0 versus 1), and macro-vascular invasion (yes versus no). The effect of Arm C vs. Arm D will be estimated by the HR together with its corresponding 95% CI and p-value.

The key secondary analyses are to compare OS for Arm A vs. Arm D (for non-inferiority, then superiority) in the FAS (ITT) analysis set.

The comparison of OS for Arm C vs. Arm A in the FAS (ITT) analysis set is a secondary analysis.

Secondary OS analyses will be performed using the same methodology as for the primary analysis described above.

[figure not shown]
Kaplan-Meier plots of OS will be presented by treatment arm. Summaries of the number and percentage of patients who have died, still in survival follow-up, lost to follow-up, and have withdrawn consent will be provided along with the median OS for each treatment.

The assumption of proportionality of hazard will be assessed first by examining plots of complementary log-log (event times) versus log (time) and, if these raise concerns, by fitting a time-dependent covariate to assess the extent to which this represents random variation. If a lack of proportionality of hazard is evident, the variation in treatment effect will be described by presenting piecewise HR calculated over distinct time periods. In such circumstances, the HR can still be meaningfully interpreted as an average HR over time unless there is extensive crossing of the survival curves. If lack of proportionality of hazard is found, this may be a result of treatment-by-covariate interactions, which will be investigated. In addition, the Kaplan-Meier curve along with landmark analyses (eg, 18-, 24-, and 36-month OS rate) will also help in understanding the treatment benefit.

[figure not shown]
A sensitivity analysis for OS will examine the censoring patterns to rule out attrition bias, achieved by a Kaplan-Meier plot of time-to-censoring where the censoring indicator of OS is reversed.

The superiority boundary (ie, adjusted alpha levels) for the HR of treatment comparison at the interim and the final for the primary OS analysis will be derived based on the exact number of OS events using the Lan and DeMets approach that approximates the O'Brien Fleming spending function (see Section 8.5.1).

[figure not shown]
CCI

CCI

CCI

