## Statistical methods

### *Efficacy analyses*

The primary endpoint of this study is OS. The secondary endpoints are ORR, DCR, DCR-16w, DCR-24w, DoR, PFS, TTP, OS18, OS24 and OS36. CCI

All tumor-assessment-related endpoints will be analyzed using Investigator assessments according to RECIST 1.1.

Efficacy data will be summarized and analyzed on an intent-to-treat (ITT) basis, and the treatment arms will be compared on the basis of randomized treatment, regardless of the treatment actually received. Patients who are randomized but do not subsequently go on to receive study drug(s) are included in the ITT population.

Two interim analyses and a final analysis are planned as described below:

Interim Analysis 1 (IA1): The first interim analysis will be performed after approximately 100 patients per treatment arm have had the opportunity for 32 weeks of follow-up. The objective is to evaluate the efficacy of Arm A and Arm C in terms of ORR and DoR. The efficacy analysis set will include all randomized patients who have had the opportunity for at least 32 weeks of follow-up at the time of the IA1 data cutoff (ie, randomized  $\geq$  32 weeks prior to IA1 DCO). Descriptive summaries of ORR including exact 95% confidence intervals (CIs) will be presented. Kaplan-Meier plots of DoR and median DoR derived from the KM curves will also be provided. No formal comparison between arms will be performed in this interim analysis.

Interim Analysis 2 (IA2): The second interim analysis will be performed when approximately 404 OS events have occurred in Arm C and Arm D combined (~52% maturity) approximately 30 months after the first patient is randomized. The goal is to evaluate the efficacy of Arm C vs. Arm D in terms of OS (for the primary objective of superiority) and Arm A vs. Arm D in terms of OS (for the key secondary objectives – first for non-inferiority and then for superiority). OS will be analyzed using a stratified log-rank test (stratified for macro-vascular invasion, etiology of liver disease, and ECOG performance status). The treatment effect will be estimated by the hazard ratio (HR) together with its corresponding 95% confidence interval (CI) and p-value for each comparison.

Enrollment must be completed before Interim Analysis 1 can be performed.

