***Durvalumab [REDACTED] mg monotherapy (Arm A) versus sorafenib [REDACTED] mg [REDACTED] (Arm D) - OS in FAS ITT***

It is estimated that approximately 453 and 560 events can be observed at the time of the interim and final analysis respectively. The power of the NI test at margin of 1.08 is approximately 84% at final analysis.

- The noninferiority margin of HR 1.08 is determined using 95%-95% fixed margin approach (FDA Guidance 2016; EMEA Guideline 2005) based on two phase 3 trials of sorafenib (Llovet 2008 and Cheng 2009) in first line HCC and assuming conservative 60% retention. Multiple historical trials in the same indication were also designed as NI

- using including Brivanib (Johnson 2013), Sunitinib (Cheng 2013), Linifanib (Cainap 2014), and Lenvatinib (Kudo 2017).

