**CCI**

### 8.5 Methods for statistical analyses

The formal statistical analysis of OS (primary endpoint) will be performed for the following efficacy test hypotheses (alternative hypotheses):

- $H_1$ : Difference between durvalumab **CCI** mg plus tremelimumab **CCI** mg **CCI** (Arm C) and sorafenib **CCI** mg **CCI** (Arm D)
- $H_2$ : Durvalumab **CCI** mg monotherapy (Arm A) not inferior to sorafenib **CCI** mg **CCI** (Arm D) with noninferiority margin of 1.08
- $H_3$ : Difference between durvalumab **CCI** mg monotherapy (Arm A) and sorafenib **CCI** mg **CCI** (Arm D)

Efficacy data for Arm B: durvalumab **CCI** mg plus tremelimumab **CCI** mg **CCI** combination therapy arm (which was closed for enrollment with Amendment 4) will be summarized descriptively, but will not be formally analyzed.

Descriptive statistics will be used for all variables, as appropriate, and will be presented by treatment arm. Continuous variables will be summarized by the number of observations, mean, standard deviation, median, minimum, and maximum. Categorical variables will be

summarized by frequency counts and percentages for each category. Unless otherwise stated, percentages will be calculated out of the population total for the corresponding treatment arm.

Baseline will be the last assessment of the variable under consideration prior to the intake of the first dose of treatment, except for efficacy variables. For efficacy variables, baseline is defined as the last visit prior to randomization.

All data collected will be listed. Efficacy and PRO data will be summarized and analyzed based on the FAS (intent-to-treat [ITT] population). PK data will be summarized and analyzed based on the PK analysis set. Safety data will be summarized on the safety analysis set.

Results of all statistical analysis will be presented using a 95% confidence interval (CI) and 2-sided p-value, unless otherwise stated.

**Table 16** details which endpoints are to be analyzed, together with pre-planned sensitivity analyses indicating which analysis is regarded as primary for that endpoint.

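### Does describing the non-inferiority comparison with the superiority log-rank test and a 95% CI leave H2 without a valid test, or inflate its type I error?

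*Protocol*

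**What the plan says.** Section 8.5 lists H2 as Arm A not inferior to sorafenib, the entry closing "Arm D) with noninferiority margin of 1.08". Section 8.2 gives the planning figures: "It is estimated that approximately 453 and 560 events can be observed at the time of the interim and final analysis respectively", and "The power of the NI test at margin of 1.08 is approximately 84% at final analysis". On the margin it says "The noninferiority margin of HR 1.08 is determined using 95%-95% fixed margin approach".

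The analysis method is described in superiority terms. The synopsis lists the non-inferiority objective at IA2 and then states "OS will be analyzed using a stratified log-rank test", with an HR, 95% CI and p-value for every comparison; the final analysis follows the same method. Section 8.5.2.1 says of the primary comparison "The effect of Arm C vs. Arm D will be estimated by the HR together with its corresponding 95% CI and p-value", names the Arm A versus Arm D comparisons as key secondary and Arm C versus Arm A as secondary, and adds "Secondary OS analyses will be performed using the same methodology as for the primary analysis described above".

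On error control, section 8.5.1 reserves 4.9% (two-sided) for all OS analyses together, uses Lan-DeMets O'Brien-Fleming-type spending for H1, and gives the resulting levels: "the 2-sided significance levels to be applied for the interim and final OS analyses would be and 0.0222 and 0.0425, respectively". It commits to strong type I error control through the procedure in Figure 5 (not reproduced in the copy reviewed), with details in the SAP.

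**The concern.** Three features invite the objection. First, a log-rank test has null HR = 1, so its p-value does not address whether the HR is below 1.08. Second, the only visible quantity that could be compared with 1.08 is the 95% CI, which is prescribed at both OS looks; 95% is not the level matching 0.0222 or 0.0425. Third, the spending function is set out for H1, and section 8.5.2.1 describes the adjusted boundary as one for superiority in the primary OS analysis.

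H2 is a key secondary hypothesis and comes before H3 in the testing order. If its test had the wrong null, the stated power would not be delivered. If an unadjusted 95% CI decided it at both looks, the error for a formal claim would exceed its allotment.

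**Working it through.** **Inputs.** Margin 1.08 (section 8.5); Arm A plus Arm D events 453 and 560 (section 8.2); OS alpha 4.9% two-sided, that is 2.45% per side; levels 0.0222 and 0.0425 at 404/515 events (section 8.5.1); 1:1 allocation. The true HR assumed for Arm A versus Arm D is not given, so a range is used below.

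**1. The plan's own levels.** Spending per side at information fraction t is 2 − 2Φ(z/√t), with z the normal quantile at 1 − 0.0245/2. With t = 404/515 = 0.784 this gives a two-sided interim level of 0.0222. Solving P(Z1 > c1 or Z2 > c2) = 0.0245 with correlation √t gives a final level of 0.0425. Both stated figures reproduce.

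**2. Which test was powered?** With 560 events:
- Test against 1.08: power = Φ(√(560/4) × (ln 1.08 − ln HR) − 2.028). At the 0.0425 level this is 93.6% at HR 0.80, 82.8% at 0.84, 79.0% at 0.85 and 55.1% at 0.90. It equals 84% at HR of about 0.836.
- Log-rank test of HR = 1, at HR 0.84: about 51%.

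Section 8.2 attaches its 84% to a test at the margin. The shifted test reaches that figure at a true HR of about 0.84, where the unshifted test would have only about 51%.

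**3. The literal log-rank reading.** If H2 were declared only on a significant log-rank test of HR = 1, the chance of a positive result at the final analysis with true HR 1.08 is Φ(−2.028 − √(560/4) × ln 1.08) = Φ(−2.94), about 0.16%. That is conservative, and it makes H2 the same test as H3. It does not inflate error.

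**4. The plain 95% CI reading.** At true HR 1.08 the correlation between looks is √(453/560) = 0.899.

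| Rule for H2 | One-sided error (allotted 2.45%) |
|---|---|
| 95% CI at both looks | 3.52% (7.04% two-sided equivalent) |
| 95% CI at the final analysis only | 2.50% |
| Stated levels 0.0222 / 0.0425 | 2.42% |
| H2's own spending at t = 0.809: 0.0248 / 0.0418 | 2.45% |

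A simulation of the first row gave 3.53%.

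**5. Observed HR needed for non-inferiority**, from 1.08 × exp(−2z/√events):

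| Look | Plain 95% CI | Adjusted level |
|---|---|---|
| IA2, 453 events | 0.898 | 0.871 to 0.875 |
| Final, 560 events | 0.915 | 0.909 to 0.910 |

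**6. Does the text adopt the first rule?** The 95% CI appears in the synopsis and section 8.5.2.1 as the way the effect is estimated, and in section 8.5 as the general presentation format. The same wording covers H1, which section 8.5.1 decides at 0.0222 and 0.0425. Reporting a 95% CI therefore cannot by itself imply a 5% decision level. The 95%-95% phrase in section 8.2 describes how the margin was derived, not how H2 is decided at each look.

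**The case for a change.** The strongest case for a change is that the protocol does more than stay silent: it assigns a method. The synopsis attaches the log-rank test and 95% CI to each comparison straight after naming non-inferiority, and Table 16 lists only the stratified log-rank test as the primary OS analysis. A general promise of strong control does not correct a test with the wrong null, and a literal analyst would have about 51% power at HR 0.84 where section 8.2 implies about 83%.

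Part of this stands. No visible sentence says how 1.08 enters the test, and a 95% CI is not the interval that matches the adjusted levels. The arithmetic for a 95% CI used at both looks is also right.

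The rest does not carry. H2 is stated against 1.08 and powered as a test at 1.08, so an SAP that compares the interval with 1.08 implements the hypothesis rather than departing from it. The two complaints also rest on incompatible readings: the literal log-rank reading is conservative, and only the unstated 95% CI rule inflates. That rule would conflict with the 4.9% cap that section 8.5.1 places on all OS analyses. Finally, the sentence about secondary OS analyses follows the Arm C versus Arm A comparison, and the protocol separates key secondary from secondary objectives, so it may not refer to H2 at all.

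**Conclusion.** The concern does not call for a change. The visible text leaves unwritten that H2 is judged by the upper limit of the stratified HR's confidence interval, at the look-specific adjusted level, against 1.08. That is detail a protocol commonly leaves to the SAP, and an analyst reading sections 8.2, 8.5 and 8.5.1 together would supply it.

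Under that reading the one-sided H2 error is 2.42% with the stated levels, or 2.45% with H2's own spending, against 2.45% allotted. The 3.52% figure needs a decision rule the protocol does not state. Even then the final-analysis cut-off would move only from 0.909–0.910 to 0.915; the larger difference is at IA2 (0.871–0.875 against 0.898).

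This conclusion assumes the planned 453 and 560 events, the normal approximation for the log hazard ratio, and that Figure 5 and the SAP, neither available for this review, carry out the strong control that section 8.5.1 promises. If the SAP instead let an unadjusted 95% CI decide H2 at both looks, the fault would lie there and the 3.52% would apply.

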### **8.5.3 Analysis of the secondary variable(s)**

#### **8.5.3.1 Progression-free survival**

Analysis of PFS (per RECIST 1.1 using Investigator assessments) will be performed to compare Arm A vs. Arm D and Arm C vs. Arm D as well as to compare Arm C vs. Arm A using the same methodology as for OS.

#### **8.5.3.2 Time to progression**

Analysis of TTP will be performed to compare Arm A vs. Arm D and Arm C vs. Arm D as well as to compare Arm C vs. Arm A using a stratified log-rank test as described for OS.

#### **8.5.3.3 Objective response rate**

At IA1, only descriptive summaries of ORR including exact 95% CIs will be presented for each treatment arm (Arm A and Arm C). The analysis set will include all randomized patients who have had the opportunity for at least 32 weeks of follow-up at the time of the IA1 data cutoff (ie, randomized  $\geq 32$  weeks prior to IA1 DCO). ORR results will be presented by Investigator assessment (using RECIST1.1) and BICR (using RECIST1.1 and mRECIST).

At the final analysis, the ORR (per RECIST 1.1 using Investigator assessments) will be compared between Arm A vs. Arm D and Arm C vs. Arm D as well as to compare Arm C vs. Arm A. Logistic regression models adjusting for the same factors as the primary endpoint (etiology of liver disease, ECOG, and macro-vascular invasion) will be fitted. The results of the analysis will be presented in terms of an odds ratio together with its associated 95% CI and p-value. This analysis will be performed in the FAS (ITT) analysis set.

Summaries will be produced that present the number and percentage of patients with a tumor response (CR/PR). Overall visit response data will be listed for all patients (ie, the FAS). For each treatment arm, best objective response (BoR) will be summarized by n (%) for each category (CR, PR, SD, PD, and NE). No formal statistical analyses are planned for BoR.

#### **8.5.3.4 Disease control rate**

The DCR, DCR-16w and DCR-24w based on Investigator assessments per RECIST 1.1 will be summarized (ie, number of patients [%]) per treatment arm.

#### **8.5.3.5 Duration of response**

Descriptive data will be provided for the DoR based on Investigator assessments per RECIST 1.1 in responding patients, including the associated Kaplan-Meier curves (without any formal comparison of treatment arms or p-value attached). This analysis will be performed in the FAS (ITT) analysis set.

### 8.5.3.6 OS18,OS24 and OS36

OS18,OS24 and OS36, along with their 95% CI, will be summarized (using the Kaplan-Meier curve) and presented by treatment arm. The HR and CI will be presented using the method described by Klein et al ([Klein et al 2007](#)).

This analysis will be performed in the FAS (ITT) analysis set.

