## 4.3 Follow-up period

Patients who are permanently discontinued from further receipt of study drug(s), regardless of the reason, will be identified as having permanently discontinued treatment and will enter follow-up ([Table 4](#)).

Patients who permanently discontinue drug for reasons other than objective RECIST 1.1 disease progression should continue to have RECIST 1.1 scans performed Q8W ( $\pm 1$  week) for the first 48 weeks relative to the date of randomization and then Q12W ( $\pm 1$  week) thereafter until confirmed PD as defined in [Table 4](#).

Whenever vital signs and blood draws are scheduled for the same nominal time, the assessments should occur in the following order: vital signs, and then blood draws. The timing of the first 2 assessments should be such that it allows the blood draw (eg, PK blood sample) to occur at the timepoints indicated in [Table 4](#).

All patients will be followed for survival until the end of the study. Following the final primary analysis, which will include all study endpoints, the study database may remain open for collection of long term follow-up as presented in Table 22 in section 9.3.

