## **8.2 Sample size estimate**

The study will plan to screen approximately 1650 patients in order to randomize approximately 1310 eligible patients in the global study. (This includes 1155 patients randomized to Arms A, C, D with 385 per arm; and approximately 155 patients in Arm B, randomized prior to the closure of this arm. Patients from China enrolled in the global study are included in this figure). Once global enrolment has completed, recruitment into an expansion cohort will continue in China (ie. China Tail) until a total of 180 Chinese patients have been randomized. Patients from China enrolled in the global study and the China Tail will be included in a China cohort. Details of the China cohort and analysis plan will be outlined in a China specific amendment and SAP. Patients will be randomized 1:1:1:1 to durvalumab [redacted] mg monotherapy (Arm A), durvalumab [redacted] mg plus tremelimumab [redacted] mg [redacted] combination therapy (Arm B), durvalumab [redacted] mg plus tremelimumab [redacted] mg [redacted] combination therapy (Arm C), or sorafenib [redacted] mg [redacted] (Arm D). Following Amendment 4 Arm B will be closed for enrollment therefore new patients will be randomized in a 1:1:1 ratio into Arm A, Arm C, and Arm D.

The study is sized to characterize the OS benefit of Arm C vs. Arm D.

The sample size estimation assumes an exponentially distributed OS and a 2-month delay in separation of the OS curves for Arm C vs. Arm D, hence the use of average HR (0.70 for Arm C vs. Arm D). A non-uniform accrual (weight=2) of patients with a duration of 22 months is assumed when estimating the analysis times with a follow-up duration of 15.5 months and a total duration of 37.5 months. No adjustment has been included for dropouts.

For the efficacy comparisons, the median OS for sorafenib (Arm D) is assumed to be 11.5 months, with an 18-month OS rate of 33.8%.

***Durvalumab [REDACTED] mg plus tremelimumab [REDACTED] mg [REDACTED] (Arm C) versus sorafenib [REDACTED] mg [REDACTED] (Arm D) - OS in FAS intent-to treat (ITT)***

The assumed OS treatment effect is an average HR of 0.70 for Arm C versus Arm D. This translates to an increase in median OS from 11.5 months to 16.5 months and in the 18-month OS rate from 33.8% to 46.8% in Arm C versus Arm D.

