At the time of the second Interim Analysis (IA2), the analysis of OS will be performed when approximately 404 OS events in Arm C and Arm D combined (~52% maturity) have occurred, approximately 30 months after the first patient is randomized. This number of OS events will provide 85% power to demonstrate a statistically significant difference in OS at a 2-sided 2.22% significance level.

Final analysis of OS will be performed when approximately 515 events in Arm C and Arm D combined (~67% maturity) have occurred, approximately 37.5 months after the first patient is randomized. This number of OS events will provide 97% power to demonstrate a statistically significant difference in OS at a 2-sided 4.25% significance level. The smallest treatment difference that could be observed as statistically significant at the final analysis is an average HR of 0.84 (an increase in median OS from 11.5 months to approximately 13.7 months in Arm C versus Arm D).

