***Proportion of patients alive at 36 months after randomization (OS36)***

**8.4.2 The OS36 will be defined as the KM estimate of OS at 36 months after randomization.Calculation or derivation of safety variables**

Safety and tolerability will be assessed in terms of AEs (including SAEs), deaths, laboratory data, vital signs, ECGs, and exposure. These will be collected for all patients. Data from all cycles of treatment will be combined in the presentation of safety data. “On treatment” will be defined as assessments between date of start dose and 90 days following discontinuation of study drug(s) (ie, the last dose of durvalumab, tremelimumab, or sorafenib). For AEs, on treatment (or treatment-emergent AEs) will be defined as any AEs that started after dosing or prior to dosing and which worsens following exposure to the treatment.

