## **9.3      Study timetable and end of study**

The study will remain open until the last patients' treatment discontinuation.

The study is expected to start in Q4 2017 and to end by Q4 2021 (final primary analysis). Long-term follow-up data may be collected in eCRFs post final primary analysis for approximately 5 years, as outlined in Table 22.

Long-term follow-up: Subjects continuing treatment should be followed for below assessments Q4W (+/- 1 week). Subjects who have discontinued from treatment should be followed for below assessments Q8W (+/- 1 week). All SAEs and reports of pregnancy experienced by patients whilst receiving treatment or within 90 days of treatment discontinuing must continue to be reported to the Sponsor within the usual timelines (ie, immediately, or no later than 24 hours of when the site become aware of the SAE) directly in the EDC. If long-term follow-up is collected post final primary analysis, then the end of study is defined as the last visit of the last patient in the study.

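### Is OS36 set for a final analysis that comes too early to estimate survival at 36 months?

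*Protocol*

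**What the plan says.** OS36 is a secondary outcome for Arm A versus D and Arm C versus D (Section 2.3). Under the secondary endpoints in Section 8.4.1.3, "The OS36 will be defined as the KM estimate of OS at 36 months after randomization". Table 16 adds a comparison, "Hazard ratio using the KM estimates of OS at 36 months", and Section 8.5.3.6 gives the presentation: "OS18,OS24 and OS36, along with their 95% CI, will be summarized (using the Kaplan-Meier curve) and presented by treatment arm". Neither place names a data cutoff.

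Section 4.3 does link the endpoint to a time: "Following the final primary analysis, which will include all study endpoints", it says, before allowing the database to stay open for long-term follow-up.

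The timing of that analysis appears in three forms:

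- As an event trigger, in Section 8.2: "approximately 515 events in Arm C and Arm D combined (~67% maturity) have occurred". The synopsis and Section 8.5.1 use the same trigger.
- As a projected time, in Section 8.5.1: "approximately 37.5 months after the first patient is randomized". Section 8.2 shows where this comes from. Accrual over 22 months with weight 2 is assumed for estimating the analysis times, "with a follow-up duration of 15.5 months and a total duration of 37.5 months".
- As a calendar date, in Section 9.3: "The study is expected to start in Q4 2017 and to end by Q4 2021 (final primary analysis". The same section allows about 5 more years of long-term follow-up, and Table 22 includes a survival assessment.

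**The concern.** Read together, Sections 4.3, 8.2 and 8.5.1 seem to place OS36 at month 37.5. Only patients randomized in the first 37.5 − 36 = 1.5 months could have been observed to month 36 by then, and weight-2 accrual puts very few patients there. The Kaplan-Meier curve would usually stop short of month 36 in at least one arm, and a fixed-time hazard ratio needs an estimate in both.

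If so, a listed secondary endpoint would be undefined at the analysis said to contain it. Section 8.5.2.1 also names the 36-month rate among the landmarks that help interpret non-proportional hazards, and the design itself assumes a 2-month delay in separation of the curves. Section 9.3 gives a date that does not match 37.5 months, and no section assigns OS36 to the long-term follow-up.

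**Working it through.** **Inputs (Section 8.2).** 385 patients per arm. Accrual over 22 months with weight 2, read as a cumulative share of (t/22)². Arm D exponential with median 11.5 months. Arm C median 16.5 months after a 2-month delay. No dropout.

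**Step 1. Reproduce the plan's own figures.** The Arm D hazard is λ = ln 2 / 11.5. Arm C has that hazard for 2 months, then λ multiplied by (11.5 − 2)/(16.5 − 2) = 9.5/14.5 = 0.655, which gives a median of 16.5. Expected deaths per arm at time T are 385 × ∫₀²² (2s/22²)[1 − S(T − s)] ds. Summed over Arms C and D:

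- T = 30: 404.4 (stated 404)
- T = 37.5: 515.3 (stated 515)

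The accrual reading is therefore the protocol's own, and 37.5 months is the month at which the model expects 515 deaths.

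**Step 2. OS36 at exactly 37.5 months.** Patients per arm with 36 months of potential follow-up: 385 × (1.5/22)² = 1.8. With S(36) = 0.114 in Arm D and 0.231 in Arm C, the expected numbers at risk are 0.2 and 0.4. In 1,000 simulated trials per arm, the Kaplan-Meier estimate at month 36 was defined in about 26% (D) and 37% (C). At that cutoff the worry would be justified.

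**Step 3. The stated calendar date.** From the last day of Q4 2017 to the first day of Q4 2021 is about 45 months; from first day to last day is about 51. Potential follow-up of at least 36 months is 385 × ((T − 36)/22)² patients per arm, and the number at risk is that count multiplied by S(36).

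| T (months) | Per arm with 36 months possible | At risk, D | At risk, C | KM defined in simulation | SE, D (points) | SE, C (points) |
|---|---|---|---|---|---|---|
| 45 | 64 | 7 | 15 | always | 2.3 | 2.9 |
| 48 | 115 | 13 | 27 | always | 2.0 | 2.5 |
| 51 | 179 | 20 | 41 | always | 1.8 | 2.3 |

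At month 48 the 95% interval is about 11.4% ± 1.96 × 2.0 = ± 3.9 points in Arm D, and 23.1% ± 1.96 × 2.5 = ± 4.9 points in Arm C. These are usable intervals.

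**Step 4. Was OS36 ever meant for month 37.5?** The version history, used here only for dating, shows that OS36 entered with Version 7 on 22 September 2021. The same version clarified Q4 2021 as the final primary analysis and added long-term follow-up. For any start in Q4 2017, month 37.5 had passed by about mid-February 2021 at the latest. OS36 was thus written in when the projected month was already past and the analysis was dated Q4 2021.

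**Step 5. Sensitivity to slower accrual.** On the planned assumptions 515 deaths fall at month 37.5, so a Q4 2021 cutoff suggests slower accrual or fewer deaths than planned. As an assumption for illustration, stretch the same accrual shape to 30 months. At T = 45 the count is 385 × (9/30)² = 35 per arm, with 35 × 0.114 = 4 at risk in Arm D and 35 × 0.231 = 8 in Arm C. At T = 51 it is 385 × (15/30)² = 96 per arm. Precision falls, but there are still patients to estimate from. Fewer deaths would instead raise the numbers at risk.

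**The case for a change.** The strongest case is that the protocol places OS36 at the final primary analysis through Section 4.3 and then gives two timings for that analysis that do not agree. At one of them OS36 is usually undefined; at the other it is estimable. Version 7 left 37.5 months in the synopsis and in Sections 8.2 and 8.5.1. Long-term follow-up is optional, and no passage ties OS36 to it. A reader of those sections alone could be misled.

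Part of this stands: the two timings differ by about 45 − 37.5 = 7.5 to 51 − 37.5 = 13.5 months, and the text does not reconcile them. But they do not have equal standing. The cutoff is governed by the event count, which is the same throughout; 37.5 months is a forecast of when that count is reached, and Section 9.3 carries the date attached to the final primary analysis.

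Which cutoff reports which landmark is commonly left to the SAP, which was not available for this review. Section 5.1.2 already provides for survival contacts at the primary analysis and at later survival analyses. Nor is there a need to hold OS36 until every patient has 36 months of potential follow-up, at month 22 + 36 = 58. Kaplan-Meier handles administrative censoring, and waiting would only delay an endpoint that is estimable at the stated date.

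**Conclusion.** The concern does not hold. It treats a planning projection as the analysis date. At the date the current protocol gives, 64 to 179 patients per arm have 36 months of potential follow-up, and OS36 is estimable with a standard error of about 1.8 to 2.9 percentage points. This rests on a Q4 2017 start, a Q4 2021 cutoff, and the planned accrual and survival; slower accrual would lower the counts, as shown.

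The stakes are also limited. OS36 is not among H1 to H3, so the primary conclusion, alpha and power are unaffected. For non-proportional hazards, Section 8.5.2.1 also offers piecewise hazard ratios and the 18- and 24-month rates. The unreconciled 37.5-month projection beside Q4 2021 is clerical: the event trigger governs, and no result changes.
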